Effects of a Cognitive Interference Task on Alcohol Craving and Consumption Among Women

NCT number NCT04924283
Document Date 02/15/2022

Effects of a Cognitive Interference Task on Alcohol Craving and Consumption among Women ([name], Assistant Professor, Dept. of Psychiatry)

Despite the prevalence and serious consequences of alcohol use disorder (AUD) among women, only 5.4% receive treatment.¹ Brief mobile interventions are a promising way to deliver accessible, evidence-based interventions to women who would not otherwise seek help. The primary objective of the proposed study is to test the effects of a brief, cognitive interference task (Tetris) in reducing alcohol craving and consumption among women with at-risk drinking according to NIAAA guidelines.³ Elaboration Intrusion Theory (EIT) proposes that visual working memory processes are central to craving, and that imagined experiences of engaging in substance use increases motivation to engage in the actual behavior.⁴ In laboratory and real-world settings, participants report decreased craving for food and substances after completing Tetris, a visuospatial task that increases the demands of working memory processes.⁵⁻⁶ Based on previous research, the current study will collect ecological momentary assessment (EMA) data for a 1-week baseline period, followed by a 2-week intervention phase in which participants will be randomly assigned to the experimental condition (Tetris) or a control condition (assessment only). During the intervention phase, participants will receive a combination of event- and signal-contingent EMA assessments, and the experimental condition will also receive daily prompts to complete Tetris in-between assessments. EMA will be used to assess alcohol craving and consumption during the baseline and intervention phase and deliver the intervention in real-time.

Specific Aim 1: Evaluate the effects of a brief cognitive interference task on alcohol craving among women who report at risk drinking. Hypothesis: Participants in the experimental group, relative to controls, will evidence significantly lower craving 1) immediately after completing the task, and 2) during the 2-week intervention phase.

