Specific Aim 2: Evaluate the effects of a brief cognitive interference task on alcohol consumption, as measured by self-report among women who report at risk drinking. Hypothesis: Participants in the experimental group, relative to controls, will demonstrate significantly lower consumption of alcohol (fewer standard drink units) during the 2-week intervention phase and at 1-month follow-up.

Approach

Participants: Forty women who report at risk drinking will be recruited nationally from online campaigns, the community, and locally from the Women's Health Clinic at the Medical University of South Carolina (MUSC). Many women use obstetricians and gynecologists (OB/GYN) as their primary resource for behavioral health care making OB/GYN health care settings an ideal place to provide accessible interventions for AUD to women.² The inclusion criteria for alcohol consumption will be having a positive score on the AUDIT-C (i.e., a score of 3 or greater) at the time of screening. Additional inclusion criteria include: 1) female, any race or ethnicity; 2) ages 21-65; 3) able to comprehend English to provide informed consent and complete the assessments. Exclusion criteria include: 1) currently engaged in treatment for AUD; 2) current clinically significant bipolar affective disorder, schizophrenia, or psychotic disorder; 3) pregnant; 4) imminently suicidal or homicidal; 5) participants taking medications known to affect alcohol craving or consumption and 6) a score of 10 or higher on the Clinical Institute of Alcohol Withdrawal Revised (CIWA-R).²⁴

Study Procedures

Initial Screening. Potential participants will complete a brief screener over the phone or via REDCap to determine initial eligibility. The brief screener will ask yes/no and multiple choice questions focused on inclusion/exclusion criteria.

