During, the experimental phase, the same assessments will be administered. In addition, any occasion in which a positive response to current craving is reported, an automated prompt will be displayed to re-rate cravings four minutes later. Participants in the experimental condition will receive an automated prompted to complete the Tetris task in-between the ratings. After four minutes the application will upload a screen shot of the Tetris game into RedCAP. The Tetris task involves manipulating basic shapes to form rows that then disappear. Participants in the experimental condition will be asked to play Tetris after CREMA sessions and after any of the three random craving assessment that participants report experiencing craving. Participants in the control condition will just be asked to re-rate craving four minutes later and report what activities they completed during the three-minute break.

Post-Experiment Assessment: Participants will complete self-report questionnaires via REDCap. In addition, participants will complete the TLFB over a video call at a 1-month follow-up. Figure 1 below illustrates the study design.

Figure 1. Study design

Statistical Analyses

To establish feasibility, descriptive analyses will be used to measure the proportion of prompts participants respond to, and the response time to complete prompts. An intent-to-treat analysis will be conducted with mixed-effects regression to test between-group differences in urge to drink after completing the task, nested within individuals. We will use a random-effects mixed modeling approach using maximum likelihood estimation to test differences in mean craving and drinking outcomes (i.e., alcohol consumption) between baseline and post-experiment. We will test differences in alcohol consumption between baseline and one-month follow-up. Participants will be modeled as random factors and the group allocation will be a fixed factor. Maximum likelihood estimation will provide unbiased estimates assuming missingness at random.¹³

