4. IMPORTANCE OF KNOWLEDGE TO BE GAINED

The potential benefits of the knowledge to be gained from the proposed study are considerable. This study proposes to test a brief visual cognitive test to reduce alcohol craving and consumption. Alcohol misuse is common and under-treatment among women. The proposed research is an essential step in informing evidence-based practices for reducing alcohol misuse among women. The plans for monitoring risk as described above warrant the conduct of this study for the knowledge that may reasonably be expected to result.

DATA AND SAFETY MONITORING (DSM)

A Data and Safety Monitoring Plan (DSMP) has been developed in accordance with the National Institutes of Health (NIH) Office of Human Research Protection (OHRP) to assure the appropriate clinical safety monitoring of study subjects participating in this study. Recruitment and safety data are monitored according to the schedule established by the monitoring board. Quality control and assurance of data entered into the database is discussed above as part of Protections Against Risk. Missing data will be considered as part of the plan for statistical analysis.

Summary of the Protocol: This application proposes to test the efficacy of a visual cognitive interference task using ecological momentary assessments to reduce alcohol craving and consumption. The primary outcomes of interest include: (1) alcohol craving, (2) alcohol consumption.

Trial Management: The study will be conducted and managed in the National Crime Victims Research and Treatment Center in the Department of Psychiatry at Medical University of South Carolina (MUSC), College of Medicine, in Charleston, SC.

Data Management and Analysis: The PI will oversee data management, quality control procedures and data analysis conducted by the PI. Data will be entered by trained research assistants directly into Redcap and exported to standard database software (SPSS; STATA). Quarterly audits of at least 10% of data entry will be completed. A detailed data analysis plan is outlined in the Statistics Analysis section of the Research Plan.

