Descriptive analyses will be used to describe the sample. Clinical outcomes of interest are defined as: (1) decrease in craving measured by a single item from the Visual Analogue Scale immediately after task completion and from baseline to 2-week intervention phase (2) decrease in number of standard drinks (amount) from baseline to 2-week intervention phase and at 1-month follow-up measured by daily reports of “how many standard drinks did you consume yesterday?”. In order to establish feasibility, descriptive analyses will be used to measure the proportion of prompts participants responded to and response time to complete prompts. Intent to treat mixed-effects regression will be conducted to test differences in craving items after completing the task, nested within individuals. We will use a random effects mixed modeling approach using maximum likelihood estimation to test differences in mean craving and drinking outcomes (i.e., alcohol consumption) between baseline and post-experiment. We will also test differences in alcohol consumption between baseline and one-month follow-up. The participants will be modeled as random factors and the group allocation will be a fixed factor. We will examine the intervention between intervention and study time (baseline versus follow-up). Maximum likelihood estimation will provide unbiased estimates assuming missingness at random. [name] will be attending a summer statistical workshop in ecological momentary assessment data analysis and receive consultation from statisticians housed within the South Carolina Clinical & Translational Research Institute to support the proposed analyses in this project.

STUDY TIMELINE

| Overview of Study Timeline | | Months | | | | |
|-------------------------------------|--|--------|---|------|----|-----|
| | | 1 | 2 | 3-11 | 12 | 13+ |
| Tasks/Activities | | | | | | |
| Study Start Up | | ↔ | | | | |
| Recruitment | | | ↔ | → | | |
| Conduct Randomized Controlled Trial | | ↔ | → | | | |
| Data Cleaning/Analysis | | | ↔ | → | | |
| Dissemination | | ↔ | → | | | |

References

- ¹Substance Abuse and Mental Health Services Administration (SAMHSA). National Survey on Drug Use and Health (NSDUH). 2015 (NSDUH-2015-DS0001) Public-Use File Dataset. Available at: <https://www.datafiles.samhsa.gov/study-dataset/national-survey-drug-use-and-health-2015-nsduh-2015-ds0001-nid16894>.

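### The two analysis sections disagree on how the 2-week and 1-month hypotheses will be tested, and neither designates an experimental-versus-control contrast as the test

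*Combined protocol and SAP*

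**What the plan says.** **Hypotheses.** Specific Aim 1 words its prediction for women assigned to Tetris as follows: "relative to controls, will evidence significantly lower craving 1) immediately after completing the task, and 2) during the 2-week intervention phase". The prediction under Specific Aim 2, also for those women against the control arm, is that they "will demonstrate significantly lower consumption of alcohol (fewer standard drink units) during the 2-week intervention phase and at 1-month follow-up". All of these are comparisons between arms.

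**Statistical Analyses section.** The immediate post-task model is to "test between-group differences in urge to drink after completing the task, nested within individuals". For the phase-level outcomes the plan is to "test differences in mean craving and drinking outcomes (i.e., alcohol consumption) between baseline and post-experiment", and drinking is compared in the same way between baseline and 1 month. On model terms it says "Participants will be modeled as random factors and the group allocation will be a fixed factor". No time term and no group-by-time term is listed.

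**Statistical Design and Power section.** This largely repeats that text and adds: "We will examine the intervention between intervention and study time (baseline versus follow-up". It also defines the clinical outcomes as decreases from baseline.

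**Which section governs.** Under Data Management and Analysis the protocol states: "A detailed data analysis plan is outlined in the Statistics Analysis section of the Research Plan". The closest match is the Statistical Analyses section, which lacks the added sentence.

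**The concern.** Three outcomes are affected: craving over the 2-week phase, drinking over the 2-week phase, and drinking at 1 month. For each, the hypothesis compares arms while the contrast named in the Statistical Analyses section compares times.

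The added sentence in Statistical Design and Power points to the right contrast but does not settle the matter. One word is wrong. It promises only to examine the term. Its parenthesis names baseline against follow-up, and elsewhere in the analysis text follow-up means the 1-month assessment, so it may not cover the 2-week phase at all.

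Both arms rate craving and log drinks daily for three weeks, after entering on a positive AUDIT-C. Self-monitoring and regression to the mean could therefore lower craving and drinking in both arms, and the control arm is there to remove such a shared fall. An analyst following the Statistical Analyses section literally could credit that fall to Tetris. If the analyst instead relied on the group coefficient averaged over all records, a real effect would be diluted by the untreated baseline week.

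**Working it through.** The plan gives no figure of its own for this point. The check has two parts: what each candidate term estimates, and how often each would reject.

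**Inputs from the documents:** 40 women randomised 1:1; 32 expected completers, so 16 per arm; 7 baseline days and 14 experimental days; alpha 0.05; a between-group effect of d = 0.50 used for planning.

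**Assumed, because the documents do not give them:** two-sided testing; one mean per woman per phase with SD 1; between-phase correlation ρ from 0.5 to 0.7; a shared drift of 0.2 or 0.3 SD. The true group effect δ is set at 0.5 SD.

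**1. What each term estimates,** with δ the true arm difference in the intervention phase and none at baseline:
- Time term, arms pooled: the common change plus δ/2. It is non-zero whenever both arms drift, even if δ = 0.
- Group term, no interaction: δ × (intervention records)/(all records). With one mean per phase this is δ × 1/2. With daily records it is δ × 14/(7 + 14) = 2δ/3.
- Group-by-phase term: δ.
- Group difference in the intervention phase adjusted for baseline: δ.

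**2. Time test when there is no group effect.** The SD of a woman's change is √(2(1−ρ)). The test is a paired t on 32 changes (31 df) with noncentrality drift × √32 / √(2(1−ρ)). For drift 0.2 and ρ = 0.6: 0.2 × 5.657 / 0.894 = 1.265, giving 23% rejection.

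| ρ | drift 0.2 SD | drift 0.3 SD |
|---|---|---|
| 0.5 | 20% | 38% |
| 0.6 | 23% | 45% |
| 0.7 | 29% | 56% |

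In simulation at ρ = 0.6 (20,000 replicates) the time test rejected 23.4% and 45.7% of the time at these two drifts. The group-by-phase test rejected 4.9% at both.

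**3. Power of the three between-group tests at δ = 0.5 SD, 16 per arm.** Each has noncentrality (quantity estimated) / (SD × √(2/16)):
- Pooled group term: estimates 0.25, SD √((1+ρ)/2), 30 df.
- Group-by-phase: estimates 0.5, SD √(2(1−ρ)), 30 df.
- Baseline-adjusted difference: estimates 0.5, SD √(1−ρ²), 29 df.

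| ρ | pooled group term | group-by-phase | baseline-adjusted |
|---|---|---|---|
| 0.5 | 12% | 28% | 35% |
| 0.6 | 12% | 33% | 40% |
| 0.7 | 12% | 42% | 48% |

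**4. Sensitivity to using daily records.** With 7 + 14 records per woman, an assumed intraclass correlation of 0.3 to 0.7 and an assumed between-woman SD of the phase change of 0 to 0.5, power at 0.5 SD is 17-35% for the pooled group term and 58-100% for group-by-phase. Here the SD unit is that of a single daily record, so these figures are not directly comparable with step 3, but the ordering is the same. With no group effect, the pooled group term rejected about 5% of the time in 4,000 simulated trials.

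**The case against.** The strongest reply is that the interaction is already in the plan. In the added sentence, a relation between intervention and study time makes sense only as an interaction, and it sits in the fuller of the two sections. A reader might infer from the Statistical Analyses section alone that the plan omits the term altogether; the documents taken together do not support that.

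Nor do they support reading group as the only fixed factor. That section says group will be a fixed factor and stops there. Its baseline-versus-post comparison needs a time term that it does not list either, so the list is plainly incomplete.

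A reader might also infer that no stated hypothesis receives a between-group test. That is wrong for the immediate post-task comparison, which the same section makes explicitly between-group. It is too strong for the pooled group term as well: under randomisation that is a valid test of the arms, and its fault is dilution.

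Finally, the rejection rates in the working require both a shared drift and an analyst who reads a pooled fall as efficacy, which the Aims' wording would contradict. The named contrast is also not well powered at 0.5 SD under the one-mean-per-phase assumptions.

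All of this stands and limits the point to a disagreement between sections. It does not remove it: the section that appears to be the designated plan lacks the contrast, and the section that has it does not assign it to any hypothesis.

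**Conclusion.** The point holds for craving over the 2-week phase and for drinking over that phase and at 1 month. The two sections describe different analyses of these outcomes, and neither names the test of the between-group hypothesis.

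The consequence depends on which text is followed. A literal baseline-versus-post test rejects in 20-29% of trials with no group effect at a shared drift of 0.2 SD, and in 38-56% at 0.3 SD. A pooled group term keeps its 5% error rate but estimates only one-half to two-thirds of the effect. At 0.5 SD its power is about 12%, against 28-42% for group-by-phase and 35-48% for the baseline-adjusted difference.

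These figures rest on 16 completers per arm, one mean per woman per phase, a correlation of 0.5 to 0.7, and a drift and true effect that are assumed. They show direction and rough size and do not forecast this trial's results. The documents do not show that a faulty model was intended or that a fall from baseline would be reported as efficacy; they leave both open.

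**What to change.** - Make the Statistical Analyses and Statistical Design and Power sections say the same thing, and keep the explicit between-group wording for the immediate post-task test in both.
- In the added sentence, change the first occurrence of *intervention* to *interaction*, and say which time points it covers.
- Name one experimental-minus-control contrast as the test for each of the three outcomes: craving over the 2-week phase, drinking over the 2-week phase, and drinking at 1 month. I would use the group difference adjusted for the baseline value already collected. The group-by-phase term is acceptable if preferred, but the two are different tests (40% against 33% power at 0.5 SD and ρ = 0.6), so one must be chosen in advance.
- For 1 month, use the same drinking instrument at baseline and follow-up. The procedures describe the TLFB interview at both times, whereas Statistical Design and Power names the daily report.
- State that pooled or within-arm change from baseline is descriptive only.

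The cost is wording in two sections and one model term, with no new data or participants. The downside is that a fall from baseline can no longer be offered as evidence of efficacy.

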1. RISKS TO SUBJECTS

[name] and co-investigators on this project have completed the Miami Collaborative IRB Training Initiative (CITI) online training. The candidate is a licensed clinical psychologist (South Carolina #1570). The investigators on the research team includes a licensed clinical psychologist ([name]) and board-certified psychiatrists (Drs. [name] and [name]) with extensive clinical research experience in alcohol use disorder (AUD), randomized clinical trials, and women’s health. All research activity, informed consents and continuing reviews will be reviewed by the MUSC IRB in compliance with 45CFR46 before the research is initiated. Continuing review will occur annually.

Human Subjects Involvement, Characteristics, and Design: A total of 40 women between the ages of 21 and 65 who report at risk drinking will be enrolled over a 1-year period. Participants will be randomly assigned (1:1) to the experimental group or an assessment-only group using a computer-generated randomization scheme ($N=20$) in the experimental condition; $N=20$ in the assessment-only condition). Ecological momentary assessments (EMA) will be used to collect baseline data on craving and alcohol consumption during a 1-week baseline phase. Participants will complete a morning assessment and receive random prompts four times per day during the hours of 2 PM – 9 PM. One of the prompts will be to complete a Cue Reactivity Ecological Momentary Assessment (CREMA). During the 2-week experimental phase, participants will continue to receive EMA prompts. In addition, when participants report alcohol cravings, they will be prompted to re-rate their cravings four minutes later. The experimental group will receive prompts to complete a Tetris task during the four-minute period. Post assessments will be completed via self-report questionnaires, followed by a 1-month follow-up assessment conducted by telephone or video conferencing.

Participants will be recruited nationally from online campaigns and from primary care, and Women’s Health at the Medical University of South Carolina using flyers and physician referral (see

Letter of Support from [name]). IRB approved research staff (e.g., [name], [name], [name]) will also meet with interested patients in a private room within Women's Health to inform them about the research study. Research staff will only meet with potential participants who indicate to someone directly involved in their clinical care (e.g., nursing staff) that they agree to talk with research staff about the study. Research staff will provide a brief overview of the study and those who are interested in learning more will be provided with a link to the online screener.

In addition, patients will be identified through EPIC to contact about interest in the study. Potential participants in EPIC will be women aged 21-65 who were seen in the past year in primary care/Women's Health and have not opted out of research. In addition, potential participants in EPIC will be identified by a diagnosis of ETOH use disorder, depression, and/or a positive screen for depression in their charts. We are using positive screen for depression as a way to identify potential participants because of the co-occurrence of alcohol misuse and depression. Potential participants identified through EPIC will be called, emailed, and mailed letters providing initial information about the study. Interested participants will complete a screener. Eligible participants will be asked to read and sign an electronic IRB-approved consent form before any study procedures are conducted. E-consent will be completed on REDCap. Participants will be sent a link to review the e-consent. Research staff will review the consent form over the phone or teleconferencing and answer any questions. Participants will be given as much time as needed to review the consent form. Participants and staff will sign the form electronically. A PDF of the completed consent form will be emailed me to participants from a secure MUSC email address. Participants will be informed that the project is completely voluntary and that they can withdraw at any time. Participants will be informed that the study is confidential and the limitations to confidentiality will be reviewed (e.g., in the case of harm to self or others). Participants will be informed that their participation will not affect their regular medical care at the clinic in any way. Participant recruitment will begin at the start of Year 1 and will continue until the targeted enrollment number has been reached ($N=40$). The inclusion/exclusion criteria are as follows:

Inclusion Criteria:

1. Female, any race or ethnicity, age 21 to 65 years old.
2. Able to comprehend English.
3. Positive AUDIT-C score (i.e., score of 3 or greater)

Exclusion Criteria:

1. Currently engaged in treatment for AUD.
2. Current clinically significant bipolar affective disorder, schizophrenia, or psychotic disorder.
3. Pregnant.
4. Imminently suicidal or homicidal.
5. Participants taking psychoactive medications that may affect alcohol craving or consumption.
6. A score of 10 or higher on the Clinical Institute of Alcohol Withdrawal Revised (CIWA-R).²⁴

No special classes of subjects, such as, pregnant women, prisoners, institutional individuals, or others will be recruited for this study.

Study Procedures, Materials, and Potential Risks

Study Procedures: Upon enrollment, participants will be given a full description of study procedures and asked to sign an electronic IRB-approved consent form before any study procedures or assessments are conducted. Participants will complete screening and a baseline visit via video conferencing on doxy.me or vidyo. Participants who meet eligibility criteria will be enrolled in the 1-week EMA assessment period, followed by a 2-week EMA experimental phase. Participants will complete post-experiment assessments via REDCap survey, and will be contacted via phone or video conferencing to complete a 1-month follow-up assessment.

All forms and consent procedures will be approved by the Institutional Review Board (IRB) at MUSC. The principal investigator, and co-investigators (Drs. [name], [name], [name]) have been very successful in recruiting patients with AUD to participate in research. Participants will be mailed a

pregnancy test. They will be asked to complete the test in privacy and show the results of the test strip on the screen to the researcher.

Sources of Materials: Data will be in the form of structured clinical interviews, self-reported questionnaires, obtained specifically for research purposes. Access to research records will be limited, as they will be maintained in a locked cabinet in the PI's locked office. All files will be code-linked (a random number will be used to link participants to their data and only the researchers will have access to the password protected file that links the participant to their code) to protect participants' privacy and anonymity. Only researchers working on this project will have access to the subjects' data. The materials will be specifically obtained for research purposes. Trained study personnel under the direct supervision of [name] will collect data. Subjects will be permitted to ask questions (at this or any other time during the study), consult with family members, and be fully informed of all aspects of the study before signing the informed consent and beginning the study.

Potential Risks: Two potential risks associated with involvement in the study include: (1) potential threats to confidentiality, and (2) potential distress from responding to questions that involve sensitive topics including alcohol use. These risks are discussed in greater detail as follows.

Confidentiality. Every effort will be made to protect participant's confidentiality and privacy. Due to the nature of some of the questions it is unlikely, although possible, that there may be instances in which confidentiality could be breached (e.g., suspected child abuse, harm to self or others). Participants will be informed of these risks prior to completing the assessments. We will make all possible efforts to protect the privacy and confidentiality of study participants by using only code-linked data in the database, and only subject number will be included on source documents. A password protected file will be saved on Box that links the subject to their code. Only the research team will have access to the password. No name, birthdate or other identifying information will be included on any assessment. Participants will be provided with a written informed consent document, which specifies the risks and confidentiality protections and limits of study procedures. Further, data will not be stored on the person's phone. Data for the EMA assessments will be stored within REDcap, an MUSC secured web-based survey system.

Distress or Discomfort. Some participants may experience distress by questions pertaining to their alcohol use. All participants will be informed at the outset that the study is voluntary, and they may terminate participation at any point. Our past and ongoing research suggests that data collection using many of these measures can be conducted without undue psychological distress or exacerbation of symptoms. This experience includes substantial research with younger and older adults, active duty service members, military Veterans, rape victims, victims of other forms of violence (e.g., natural disasters, car accidents), and work on large-scale studies asking questions about similar topics with general population samples.

In the event that subjects experience psychological distress secondary to participation, subjects will be encouraged to contact the PI ([name]). [name] is a licensed mental health care provider. Subjects will be given contact information for the [name] at the time of consent, as well as resources for local and national 24-hour hotline numbers. In addition, participants will have access to urgent care services at MUSC. The research team is comprised of licensed clinical psychologists and psychiatrists with extensive experience working with adults who have experienced significant life stressors and drug/alcohol addiction. If the candidate, assessors or project staff believes that a participant is significantly distressed by participation, the investigator team will be notified immediately, and [name] will contact the participant to assess distress and assure participant safety. If called by a participant, the PI will attempt to address all participant concerns and will set up an alternate referral for clinical services outside the project if desired.

With regard to potential alternative treatments, current "standard of care" exists in Women's Health in screening, brief, intervention, and referral to treatment. In addition, residents and psychology interns are available for behavioral health treatment. Participants will be able to participate in standard of care at Women's Health. When the study is being described to potential participants, it will be made very clear that the participants have the right to choose not to participate in the study and they will be

provided with appropriate referrals. All subjects in the study will be given a list of local resources and mental health agencies that may be helpful.

